9.2.2. Exclusion Criteria

Patients meeting any of the following criteria will not be included in the study:

1. Receipt of RZV (comparator cohorts only in the RZV 2-Dose analysis) during the 365 days prior to cohort entry, excluding the cohort entry date;
2. Diagnosis of HZ infection in the 365 days prior to cohort entry, excluding the cohort entry date;
 - Presence of a diagnosis code for HZ infection on the same date as RZV receipt (Dose 1 or Dose 2) will not be cause for exclusion from the study due to the administrative claims process;
3. Receipt of a solid organ transplant or hematopoietic stem cell transplant during the 365 days prior to cohort entry, excluding the cohort entry date;

4. In addition, patients with any of the following claims-based indicators of disease flare during the 91 days prior to cohort entry (as described in Section 9.2.3.2.1 for the RZV 2-Dose analysis, and in Section 9.2.3.2.2 for RZV ≥ 1 Dose analysis) will not be included in the study:
- Emergency room visit or hospitalization with UC as primary diagnosis (UC cohorts);
 - UC-related surgery (ie, colectomy, proctocolectomy) (UC cohorts); and
 - Emergency room visit or hospitalization with RA as primary diagnosis (RA cohorts).

[figure not shown]
In addition, patients meeting any of the following criteria will not be included in the RZV 2- Dose analysis:

5. Diagnosis of HZ infection within 28 days after but not including the cohort entry date (ie, Days [1,28]), as the follow up time will be assessed from day 29 after cohort entry date (Section 9.2.5.1); and
6. Occurrence of any censoring event (ie, disenrollment from health plan, death, end of the study period, or receipt of RZV) within 28 days after cohort entry date (Section 9.2.5.1).

Figure 2 summarizes the schematic for assessing patient eligibility, as well as assessment of covariates and outcomes, for (a) the RZV 2-Dose analysis and (b) the RZV ≥ 1 Dose analysis, with details outlined in the subsequent sections.

Figure 2. Schematic for Assessing Eligibility, Covariates, and Outcomes of RZV Initiators and Comparators in (a) RZV 2-Dose Analysis and (b) RZV ≥ 1 Dose Analysis

(a)

- a. Up to 32 day gaps in medical or pharmacy enrollment allowed
- b. Receipt of RZV exclusion applied to Comparator cohorts only
- c. Baseline conditions included: healthcare utilization, comorbid conditions, and treatment history

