9.2.5.2. RZV ≥ 1 Dose Analysis

In the ≥ 1 dose analysis, the occurrence of the primary outcome, HZ, for each cohort member will be assessed from the day after cohort entry until the first occurrence of HZ, disenrollment from the health plan, death, end of the study period, or receipt of RZV (patients in the UC comparator and RA comparator cohorts only). As patients may receive a diagnosis code for HZ on the date of RZV receipt, HZ diagnoses on the cohort entry date will not be counted as outcomes.

The occurrence of the secondary outcome, disease flare, will be assessed from the cohort entry date until the first occurrence of disease flare, disenrollment from the health plan, death, end of the study period, receipt of RZV (patients in the UC comparator and RA comparator cohorts only), or 90 days after cohort entry.

Primary and secondary outcomes will be assessed independently of one another; occurrence of the primary or secondary outcome will not lead to censoring for the other outcome. Furthermore, HZ and disease flare outcomes will be assessed in the RZV 2-Dose and Comparator 2-Dose cohorts independently of the RZV ≥ 1 Dose and Comparator ≥ 1 Dose cohorts. Onset of HZ that occurs during person-time between the first and second RZV doses will be attributed to the RZV or Comparator ≥ 1 Dose cohorts, and not the RZV or Comparator 2-Dose cohorts (see Section 9.2.2). Tofacitinib discontinuation will not censor follow-up for either the primary or the secondary outcome.

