9.3.5. Identification of Outcomes

9.3.5.1. Primary Outcome (Effectiveness)

The primary outcome for this study is the occurrence of new HZ infection. Occurrence of new HZ infection will be identified by the first presence of a diagnosis code for HZ infection (ICD-10 code: B02, Zoster [herpes zoster]) on at least one claim during follow-up. This algorithm was based on previous studies by Yawn et al.¹⁶ and Kim et al.¹⁷ which found that the positive predictive values (PPVs) for the presence of one diagnosis code for HZ were 85.2% and 86.2%, respectively, compared to the gold standard of medical record review.

Due to the administrative claims process, patients may receive a diagnosis code for HZ infection on the date of RZV receipt. For this reason, diagnostic codes for HZ infection that occur on the date of receipt of RZV will not be used to exclude prevalent cases of HZ (Section 9.2.2) and will not be counted as outcomes (Section 9.2.5).

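### In the ≥1 Dose HZ analysis, a repeat code from an episode first coded on the vaccination date counts as new HZ, mainly in the vaccinated arm

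*Protocol*

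**What the plan says.** Four rules in the protocol act together.

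- **Eligibility (Section 9.2.2).** Exclusion 2 removes patients with "Diagnosis of HZ infection in the 365 days prior to cohort entry, excluding the cohort entry date". A sub-bullet adds that a "diagnosis code for HZ infection on the same date as RZV receipt (Dose 1 or Dose 2) will not be cause for exclusion". Section 9.3.5.1 repeats that such codes "will not be used to exclude prevalent cases of HZ", and gives as the reason that, through claims administration, "patients may receive a diagnosis code for HZ infection on the date of RZV receipt".
- **Start of follow-up (Section 9.2.5.2).** In the ≥1 Dose analysis HZ "will be assessed from the day after cohort entry until the first occurrence of HZ". For the entry date itself, "HZ diagnoses on the cohort entry date will not be counted as outcomes".
- **Outcome (Section 9.3.5.1).** New HZ is the "first presence of a diagnosis code for HZ infection (ICD-10 code: B02, Zoster [herpes zoster]) on at least one claim during follow-up". No gap or episode rule is attached.
- **A guard in the 2-Dose analysis only (Section 9.2.2, exclusion 5).** Patients are removed for "Diagnosis of HZ infection within 28 days after but not including the cohort entry date (ie, Days [1,28", and HZ follow-up starts on day 29 (Section 9.2.5.1).

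In the ≥1 Dose analysis a comparator's entry date is drawn at random within the 4-week window (Section 9.2.3.2.2.2).

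**The concern.** The exemption rests on the premise that a B02 code on a vaccination date is a by-product of billing. Where that is so, nothing follows from it. Where the code instead marks real HZ, the patient enters the ≥1 Dose cohort with prevalent disease, and the next claim for that episode meets the definition of new HZ. A patient coded on day 0 and again on day 6 is a vaccine failure under the rules as written.

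The error is lopsided because of how entry dates arise, not because the written rule differs by arm: exclusion 2 omits the entry date for everyone. Vaccinees enter on a day that the protocol itself associates with B02 codes, and comparators enter on an arbitrary day. Weighting on baseline covariates does not remove this.

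The resulting bias imitates the hypothesis under study, which is that the vaccine protects less well under tofacitinib (Section 7). Few events are expected in vaccinees, so a handful of misclassified episodes would matter.

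**Working it through.** **Inputs from the protocol (Section 9.5):** background HZ rate 1.2 per 100 person-years (PY); reference VE 85%; 2,744 tofacitinib users with at least one dose; 2 comparators per vaccinee; 2,000 and 4,000 vaccinated PY as worked cases.

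**Inputs not in the protocol:** length of follow-up in the ≥1 Dose analysis, the share of vaccinees with a day-0 code, and the share of those coded again. For the middle row of the table in step 3, one year per patient is assumed (2,744 PY).

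**1. The plan's own precision figures.** At 2,000 vaccinated and 4,000 comparator PY, 48 comparator events are expected. With 8 vaccinee events, VE = 1 − (8/2,000)/(48/4,000) = 66.7%, and the upper 95% bound is 84.2% (log-Wald), 85.3% (mid-P) or 86.4% (exact). At 4,000 vaccinated PY, 14 against 96 events gives VE 70.8%, with upper bound 83.4%, 83.9% or 84.6%. The effect sizes also agree: (85 − 66.7)/85 = 21.5% and (85 − 70.8)/85 = 16.7%. The rate and the 2:1 ratio are therefore read as intended. The first threshold needs the Wald interval, which does not bear on this point.

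**2. How one-sided is it?** The chance that a comparator's HZ onset falls on its random entry date is 0.012/365 = 0.0033%. Among 2 × 2,744 = 5,488 comparators that is 5,488 × 0.012/365 = 0.18 patients. A second comparator route exists if eligibility is checked only at the start of the window, as Section 9.2.3.2.1.2 can be read. With a mean of 13.5 days from window start to entry, 5,488 × 13.5 × 0.012/365 = 2.4 comparators (0.04%) could enter after an onset within the window. Sections 9.2.1 and 9.2.2 tie eligibility to cohort entry, which would remove them. The imbalance is thus mainly, but not strictly only, in the vaccinated arm.

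**3. Cost per carried-over episode.** With k carried-over episodes and a comparator rate of 0.012,

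VE observed = 1 − (0.15 × 0.012 × PY + k)/(0.012 × PY) = 85% − k/(0.012 × PY).

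| Vaccinated PY | True events at VE 85% | Loss per episode (points) | VE, k = 1 | k = 2 | k = 5 |
|---|---|---|---|---|---|
| 2,000 | 3.6 | 1/24 = 4.2 | 80.8% | 76.7% | 64.2% |
| 2,744 | 4.9 | 1/32.9 = 3.0 | 82.0% | 78.9% | 69.8% |
| 4,000 | 7.2 | 1/48 = 2.1 | 82.9% | 80.8% | 74.6% |

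At 2,000 PY, 8 − 3.6 = 4.4 carried-over episodes would move a true 85% to the 66.7% that the plan uses as its threshold. UC and RA are analysed separately (Section 9.7.3.2), so PY per analysis is smaller and the loss per episode in that analysis is larger.

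**4. Would another planned analysis show it?** Section 9.7.4 varies tofacitinib exposure and dose, calendar period, dual diagnosis, prior zoster vaccination and flare definition, and adds a bias analysis for unmeasured confounding. The HZ analysis stratified by available follow-up groups patients by how long they are observed; it does not isolate early events. None of these separates repeat codes of a day-0 episode.

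**The case against.** The exemption is deliberate. The protocol gives a reason for it, and Section 5 records that it was clarified after regulatory feedback. No figure in the document shows that day-0 codes mark real disease. This stands, and it is why the size must be left open.

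Anyone with a B02 code in the preceding 365 days is already excluded, so ongoing HZ care with an earlier code does not enter. What remains is HZ first coded on the vaccination day, or care after a code-free year. By chance alone, onset on that day would affect 2,744 × 0.012/365 = 0.09 vaccinees. A much larger day-0 share would suggest that many of the codes are artefacts, and artefacts need not be followed by a second code. This also stands: a large share cannot simply be paired with a high repeat rate to produce a large bias.

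At 3.6 against 48 events, a log-Wald 95% interval around VE 85% runs from about 56% to 95%, so one or two carried-over episodes lie within random error. That is true, but the shift goes in one direction and a wider interval does not correct it.

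A reader might infer that the primary 2-Dose result is equally affected. It is not: exclusion 5 removes codes on Days 1 to 28, although its stated purpose is the day-29 start chosen for immune response, and a repeat code first seen from day 29 still gets through. A reader might also infer that follow-up from day 1 is wrong for everyone. The difficulty concerns only patients with a day-0 code.

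Finally, excluding patients because of a code after entry selects on the future, and here would act almost wholly on vaccinees. This is a fair objection to making such an exclusion part of the main analysis. It is met by placing the rule in a sensitivity analysis beside one that uses day-0 information only.

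**Conclusion.** The point holds for the ≥1 Dose HZ analysis. Followed as written, the plan can count a prevalent episode as new HZ, mainly among vaccinees, and so lower estimated VE. The direction and the mechanism follow from the text.

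The size does not. With 3.6 to 4.9 true vaccinee events (VE 85%, 1.2 per 100 PY, 2,000 to 2,744 PY), each carried-over episode costs about 3 to 4 points, and the number of such episodes is unknown. If day-0 codes are isolated artefacts, the effect is negligible. A reader might infer a specific biased VE, or that the distortion is certain to be visible. The document supports neither, because it gives no day-0 share and no repeat rate.

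Only the secondary effectiveness objective is materially exposed. The primary analysis has a small residual route through repeat codes first seen from day 29.

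**What to change.** In Sections 9.2.5.2 and 9.7.4:

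- Report, by arm, how many patients have a B02 code on the entry date, how many of them go on to an HZ outcome, and when. This count shows directly whether there is a problem.
- Pre-specify two sensitivity analyses of the ≥1 Dose HZ outcome, applied identically to both arms: (a) exclude every patient with a B02 code on the entry date, which uses no information from after entry; (b) for patients with a day-0 code, treat a further B02 code on Days 1 to 28 as the same prevalent episode and not as new HZ.

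The two complement each other. Repeat codes from day 29 escape (b) but not (a), while (b) keeps patients whose day-0 code is isolated.

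The cost is a few sentences and two further runs. Analysis (a) loses some vaccinees with artefactual codes. Analysis (b) would miss a true early HZ after an artefactual code, which at the background rate has a chance of 0.012 × 28/365 = 0.09% per such patient. The main analysis and everyone without a day-0 code are untouched.

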9.3.5.2. Secondary Outcome (Safety)

The secondary outcome for this study is disease flare: UC flare within the UC cohorts and RA flare within the RA cohorts.

For the UC cohorts, the secondary outcome will be defined by an algorithm based on the claims-based indicator of UC flare in the 90 days following the cohort entry date. Based on published literature,^{18,19} the claims-based composite algorithm of UC flare will include a combination of the following components:

- Change in UC therapy (ie, new start or switch);
 - Corticosteroids (oral, rectal, or injection);
 - 5-aminosalicylates (oral or rectal);
 - Immunosuppressants (ie, azathioprine, 6-mercaptopurine, cyclosporine, tacrolimus);
- Emergency room visit with UC as primary diagnosis;

- Hospitalization with UC as primary diagnosis;
- UC-related surgery (ie, colectomy, proctocolectomy).

For the RA cohorts, the secondary outcome will be defined by an algorithm based on the occurrence of a claims-based indicator of RA flare in the 90 days following cohort entry date. Based on published literature,^{20,21,22,23} claims-based composite algorithm of RA flare will include a combination of the following components:

- Change in RA therapy (eg, new start or switch from monotherapy to combination therapy);
 - Corticosteroids (oral or injection): initiation of, or change in, treatment with a short-acting oral glucocorticoid (eg, methylprednisolone 6-day dosing pack) or any parenteral glucocorticoid injection, excluding corticosteroids administered the same day as infusions for RA therapy;
 - Conventional synthetic disease-modifying antirheumatic drugs (csDMARDs) (ie, methotrexate, sulfasalazine, hydroxychloroquine, leflunomide);
- Emergency room visit with RA as primary diagnosis;
- Hospitalization with RA as primary diagnosis.

The claims-based indicators of disease flare will be identified based on drug (NDC and American Hospital Formulary Service [AHFS]), procedure (Healthcare Common Procedure Coding System [HCPCS], CPT[®], and International Classification of Diseases, 10th Revision, Procedure Coding System [ICD-10-PCS]), and diagnosis (ICD-10) codes. The specific codes that will be utilized to identify UC and RA disease flares are provided in [Annex 3](#).

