9.3.6.4. Treatment History

- Tofacitinib treatment;
 - Tofacitinib dose;
 - Average daily dose in prior 91 days;
 - Cumulative dose in prior 365 days;
 - Treatment duration;
- Zostavax[®] vaccination;
- TNF inhibitor treatment (eg, etanercept, adalimumab, golimumab, infliximab, certolizumab);
- Non-TNF biologics (eg, abatacept, rituximab, tocilizumab, sarilumab, anakinra, ustekinumab, vedolizumab);
- csDMARD treatment (eg, methotrexate, sulfasalazine, hydroxychloroquine, leflunomide, azathioprine);
- Immunosuppressants (eg, azathioprine, 6-mercaptopurine, cyclosporine);
- JAK inhibitor treatment (eg, baricitinib, upadacitinib);
- Corticosteroid treatment;
 - Average daily dose (eg, None, ≤ 5 mg/day, >5 to ≤ 10 mg/day, >10 to ≤ 20 mg/day, and >20 mg/day of prednisone average dose equivalent);
 - During 30 days prior to cohort entry;
 - During 365 days prior to cohort entry;
- Number of treatments for UC/RA prior to cohort entry;
- Chemotherapy;
- Radiotherapy;
- 5-aminosalicylates (eg, mesalamine, balsalazide, olsalazine);
- Ozanimod.

Additional therapies that are approved for the treatment of UC or RA may be incorporated if they become available. All of the above covariates may be considered for inclusion in the propensity score model used for IPTW.

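### The 91-day flare exclusion omits the drug starts that the flare outcome counts, so some flares already under way at entry can be recorded as new in the ≥ 1 Dose safety analysis

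*Protocol*

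**What the plan says.** **Exclusion (Protocol 9.2.2, item 4).** The item removes "patients with any of the following claims-based indicators of disease flare during the 91 days prior to cohort entry". Three entries follow. The first is "Emergency room visit or hospitalization with UC as primary diagnosis (UC cohorts"). The second is surgery for UC, and the third repeats the acute-care criterion for RA. No drug indicator appears.

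**Outcome (Protocol 9.3.5.2).** Flare over the 90 days after entry is a composite of those same acute-care and surgical events plus drug changes. For UC the drug component is "Change in UC therapy (ie, new start or switch"), covering corticosteroids, 5-aminosalicylates and immunosuppressants. For RA it is "Change in RA therapy (eg, new start or switch from monotherapy to combination therapy"), covering corticosteroids and csDMARDs, with the steroid part worded as "initiation of, or change in, treatment with a short-acting oral glucocorticoid" or any injected glucocorticoid.

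**Look-back for a drug start (end of 9.3.5.2).** For both diseases, a start or switch counts only if the same medication was not dispensed in the preceding 365 days.

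**Related provisions.** Treatment-history covariates (9.3.6.4) include average steroid dose over 365 days and "During 30 days prior to cohort entry". Other UC/RA drugs default to yes/no over the 365-day baseline (9.3.6). Section 9.7.4 plans a stricter flare definition using only surgery, emergency visits and hospitalisation.

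**The concern.** The exclusion and the outcome use different definitions of flare. A flare managed with drugs alone in the weeks before entry meets the outcome's definition but not the exclusion's. Such a patient enters the cohort while the episode may still be active, and a later event in that episode is recorded as a flare that followed the vaccination date or the comparator's index date.

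The secondary safety objectives ask whether RZV provokes flares. Episodes that began before entry cannot have been caused by a vaccine given at entry, so counting them adds events unrelated to the question. That can dilute a real signal even if both arms are equally affected. It can also distort the comparison if the arms differ in recent flare. A difference is plausible because a vaccinee's entry date is a chosen vaccination date, while a comparator's is drawn at random within a 4-week window (9.2.3.2.2).

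**Working it through.** The protocol has no flare rate, flare effect size or flare power statement (Section 9.5 is sized on HZ), so there is no figure to reproduce. The check sets the definitions side by side and then illustrates the effect with assumed values.

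**1. Components compared**

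| Component | Exclusion 4, prior 91 days | Outcome, 90 days after entry |
|---|---|---|
| ER visit or hospitalisation, primary diagnosis UC/RA | yes | yes |
| UC surgery | yes | yes |
| Corticosteroid start (UC, RA) | no | yes |
| 5-aminosalicylate or immunosuppressant start (UC) | no | yes |
| csDMARD start (RA) | no | yes |

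This reads the composite as met by any one component. Section 9.3.5.2 speaks of a combination without stating the rule.

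**2. Which carried-over flares are counted**

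Take a UC patient who starts prednisone on day −20 and is eligible.
- Prednisone refilled on day +10: not counted, because of the 365-day same-medication rule.
- Azathioprine first dispensed on day +15: counted.
- Emergency visit, admission or surgery for UC on day +15: counted.

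So the open routes are a step-up to a different listed drug, or an acute-care or surgical event.

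**3. Whether the listed covariates identify these patients**

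For steroids, partly. At an assumed 20 mg/day from day −45, the 30-day average is 20 mg and the 365-day average is 20 × 45/365 = 2.5 mg. Long-term use at that dose gives 20 and 20. The pair therefore separates a recent start from long-term use. A course that ended before day −30 gives zero at 30 days and something at 365 days whether it fell inside or outside the 91-day window. For other drugs, a yes/no over 365 days does not date the start. No listed covariate marks a drug start in the prior 91 days.

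**4. Dilution (all values assumed)**

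Let R be the true rate ratio for new flares, s the share of counted comparator flares that are carried over, and k the ratio of the carried-over flare rate, RZV to comparator. Then

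observed ratio = R(1 − s) + k·s

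| R | k | s = 5% | s = 10% | s = 20% | s = 30% |
|---|---|---|---|---|---|
| 1.5 | 1.0 | 1.475 | 1.45 | 1.40 | 1.35 |
| 1.5 | 0.5 | 1.45 | 1.40 | 1.30 | 1.20 |
| 1.5 | 1.5 | 1.50 | 1.50 | 1.50 | 1.50 |

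The signal shrinks when k is below R, is unchanged when k = R, and is inflated when k exceeds R (R = 1.25, k = 1.5, s = 30% gives 1.325).

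**5. Direction when the arms differ, with no vaccine effect (all values assumed, before weighting)**

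Let 10% of comparators and 5% of vaccinees have a drug-treated flare in the prior 91 days, and let the 90-day outcome risk be 10% in everyone else.

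- Outcome risk 40% in those patients. Comparators: 0.10 × 0.40 + 0.90 × 0.10 = 0.130. Vaccinees: 0.05 × 0.40 + 0.95 × 0.10 = 0.115. Ratio 0.115/0.130 = 0.88.
- Outcome risk 5% in those patients, because the 365-day rule blocks the drug they already had. Comparators: 0.10 × 0.05 + 0.90 × 0.10 = 0.095. Vaccinees: 0.05 × 0.05 + 0.95 × 0.10 = 0.0975. Ratio 0.0975/0.095 = 1.03.
- Equal prevalence in both arms: ratio 1.00.

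The sign depends on quantities that the protocol does not supply.

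**The case against.** The strongest reply is that the plan already handles much of this. The 365-day rule stops continued treatment from counting. Steroid dose is taken over two windows. Section 9.2.4 allows narrower windows for selected covariates, and the number of UC/RA treatments is a covariate. Section 9.7.1 allows a separate flare propensity model, with details left to the SAP. Variables still imbalanced after weighting enter the outcome model (9.7.2), and Section 9.7.4 adds a quantitative bias analysis that names disease severity. Its stricter flare definition also matches the exclusion's component types. Finally, item 4 refers to the indicators that it lists and does not claim to mirror the outcome, so nothing is contradicted.

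Most of this stands, and it narrows the point. It does not close it. The options in 9.2.4 and 9.7.1 are permissions, and none commits to a recent drug-start indicator. The stricter definition removes the drug step-up route but still counts an admission for a flare that began before entry, and it leaves the main flare analysis as it is.

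A reader might infer three stronger things that the documents do not support:
- That any continuing flare is counted as new. The same-medication rule prevents this for refills.
- That the gap makes the vaccine look safer. This needs both more recent flare among comparators and a higher countable risk in those patients. The protocol establishes neither, and the second can fail under its own 365-day rule.
- That item 4 has no place in the HZ analyses. Severity is not measured directly (9.2), so restricting on recent severe disease can limit confounding there.

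**Conclusion.** The mismatch is real and can be read directly from Sections 9.2.2 and 9.3.5.2. In the ≥ 1 Dose flare analyses some prevalent flares will be classed as incident, through step-up to a different listed drug or through an acute-care or surgical event in the same episode. This can dilute a true flare signal, and it biases the comparison if recent flare differs between chosen vaccination dates and random comparator dates. Neither direction nor size can be fixed from the documents: the figures above are illustrations that depend on the assumed carry-over share, prevalences and risks, and they ignore whatever the weighting corrects. The point concerns the secondary safety objectives only and leaves the primary HZ comparison untouched. It should be changed, since the remedy needs no new data.

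**What to change.** **Preferred.** In the flare analyses, apply the Section 9.3.5.2 drug-start indicators together with emergency visits, hospitalisation and surgery over the 91 days before entry, identically in the RZV and comparator cohorts. A full 365-day look-back for a start on day −91 would reach 91 + 365 = 456 days before entry, beyond the 365 days of enrolment that Section 9.2.1 requires. The protocol should therefore say that the available enrolment is used, which guarantees about 365 − 91 = 274 days for the earliest starts.

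**Minimum.** Add an indicator of a new listed-drug start in the prior 91 days to the flare propensity model, and repeat the flare analysis with those patients excluded.

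**Leave unchanged.** Keep item 4 as it stands in the HZ analyses.

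**Cost.** The Annex 3 code lists already exist. The flare cohort becomes somewhat smaller, from a starting count of 2,744 tofacitinib users with at least one RZV dose (RA and UC together, before eligibility criteria; Table 1). It also loses some patients whose drug change was not for a flare, a possibility that Sections 9.7.4 and 9.9 acknowledge. How many cannot be estimated from the protocol.
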